### 235 Data Collection Procedures

Volunteers will be recruited from the main campus of this tertiary care center during their 236 inpatient stay or the intake visit for cardiac rehabilitation at the main campus and satellite 237 238 facilities in the region. They may also be approached via phone call if they are on the phase II cardiac rehabilitation schedule due to receiving a referral to the program. Volunteers will be 239 screened for Facebook use and interest in the study, the protocol will be explained, and 240 volunteers will then be sent an email link to an information sheet and 2 questionnaires. The 241 information sheet will address the fact that Facebook is a public forum and names and comments 242 are seen by other participants and the research team. The Facebook group will be private in the 243 sense that those not in the group will not be able to see the content. Participants will receive a 244 baseline BREQ-3 questionnaire and PNSE scale in the email link that will follow the information 245 246 sheet. Participants will then be randomized to Facebook versus comparison groups using blocked randomization (Figure 2). 247

248

249

250

Intervention. The Facebook intervention will include peer support, education, provider support and text message prompts when new posts are added. These interventions are designed to minimize pressure, offer choices, and allow for peer interaction, positive feedback, guidance and direction, in order to provide support for competence, autonomy and relatedness. Competence will primarily be supported with use of educational posts in the Facebook group. Autonomy support will come from the provider posts. Finally, relatedness will be supported by peer interaction and engagement in the Facebook group.

a. Educational posts will cover 12 topics that will encourage participants to practice 297 298 preventive heart care while offering a variety of suggestions and encouragement 299 for making personal healthcare choices. The educational portion of the intervention is designed to offer clear information and structure, thus supporting 300 301 competence which may help to enhance intrinsic motivation. These 12 educational topics will be standardized such that they will be posted on the 302 Facebook group, one each week and then the same ones will be re-posted again 303 every 12 weeks. The posts may be in the form of text, video and/or pictures and 304 will include materials from the hospital's health library and other fact sheets and 305 videos produced by the hospital, the American Heart Association and the Center 306 for Disease Control. 307

b. Provider posts will include topics such as motivational quotes, encouragement,
reminders to exercise independently, and reminders to contact providers with
questions. These postings are designed to promote a sense of choice and help
participants feel that providers see them as having a unique frame of reference
thus being autonomy-supportive. Providers will be nurses on the research team,

313	exercise physiologists and nurse practitioners and physicians who may or may not
314	choose to reveal personal identities. All Facebook participants will see the same
315	content. Provider support will also include links to provider health chats, in
316	which patients can chat online with providers at set dates and times.
317	c. Peer interaction on Facebook will be as frequently as the participant freely
318	chooses to do so and will be monitored daily by the research team for
319	appropriateness of content. Engagement in Facebook is designed to offer an
320	opportunity for social inclusion and a sense of involvement, allowing for
321	relatedness.
322	The comparison group will receive the same educational and provider support materials
323	as the Facebook group but will receive it in the form of a handout, or via email in the event the
324	patient cannot be contacted or misses cardiac rehabilitation on a particular week. Both groups
325	will have the opportunity for weekly education classes and typical peer interactions, which will
326	involve up to 3 hours of group cardiac rehabilitation per week.
327	Upon cardiac rehabilitation completion or dropout, post-data will be collected. It is
328	anticipated that this pilot will take up to one year and will be completed when 30 participants for
329	each group have been obtained (Figure 3).
330	
331	
332	
333	

---

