### Abstract

28 While cardiac rehabilitation has been shown to be effective at improving coronary heart disease, participation is generally poor. For this reason, the current research, a prospective, randomized 29 controlled pilot study, will evaluate the impact of a social media intervention on motivation for 30 31 exercise and adherence to cardiac rehabilitation. Participants will be recruited from the inpatient 32 setting, during their intake visit to cardiac rehabilitation, or via phone call. They will then be randomly assigned to a private Facebook group or a comparison group. This study is grounded 33 in self-determination theory. The intervention will include access to a private Facebook group 34 35 in which participants will receive weekly educational posts, provider support and have the 36 opportunity to communicate with other cardiac rehabilitation patients. Postings and peer support are designed to enhance self-determined motivation through support of autonomy, competence 37 38 and relatedness. Patients in the comparison group will be given the same educational and provider materials, but these will be supplied in handout form, or email if the patient is absent 39 from cardiac rehabilitation. Participants will be asked to fill out a pre-post Behavioral 40 Regulation in Exercise Questionnaire-3, to measure self-determined motivation, and The 41 Psychological Need Satisfaction for Exercise Scale to measure fulfillment of needs that affect 42 motivation. The total number of sessions attended at the end of 3 months will be tallied and 43 analyzed using t-tests. Overall motivation will be evaluated using analysis of covariance models. 44 Multivariate analysis of variance models will be used to evaluate differences in the change across 45 motivation subtypes. If significant, ANCOVA models for each subtype will be fit. ANCOVA 46 models will be used to compare changes in needs satisfaction, overall and separately among the 47 three subscales, between groups. Engagement in the Facebook group will be measured by 48 counting number of "likes" and self-report of weekly use ("hits"). The researchers will enroll 30 49

50	participants in each group. Engagement in the Facebook group and participation in the study
51	will help to determine the feasibility of using Facebook to affect adherence and motivation in
52	cardiac rehabilitation patients, potentially improving outcomes through the use of a unique
53	intervention.

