# 144 Study Objectives

The purpose of the current randomized pilot trial is to determine the feasibility of using a Facebook intervention, providing education, peer support and provider support, to affect change in motivation and self-determination for exercise, and adherence to cardiac rehabilitation in patients with CHD during a 12-week Phase II cardiac rehabilitation program. It is hypothesized that:

150	1.	Scores for motivation for exercise overall will increase for patients exposed to a
151		Facebook intervention and across individual motivational subtypes (regulations)
152		relative to a comparison group who receive educational handouts and emails.
153	2.	Percentage of cardiac rehabilitation sessions attended will be higher relative to a
154		comparison group who receive educational handouts and emails.
155	3.	Engagement in the private Facebook group (number of "hits" and "likes") will predict
156		number of cardiac rehabilitation sessions attended and the change in motivation. The
157		feasibility of a larger trial will be based on sample size and participants' engagement
158		in the Facebook group.
159		
160		
161		

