#### 168 Setting and Sample

The setting for this study will be in the outpatient cardiac rehabilitation at the main 169 170 campus of a large tertiary care center in Northeast Ohio and several satellite facilities in the region, and in patients' homes or other locations where home computers might be accessed. This 171 cardiac rehabilitation program provides ECG-monitored, supervised exercise, dietary guidance, 172 smoking cessation, behavioral counseling and stress reduction. All patients receive an 173 individualized exercise prescription based on functional capacity at intake. Most patients, 174 depending on insurance coverage, will be able to attend up to 3 sessions per week for a total of 175 36 sessions. In addition, patients are given guidance for unsupervised exercise at home. 176

177 All patients who are current and regular Facebook users, have qualified for cardiac 178 rehabilitation (diagnosed with CHD), and are entering cardiac rehabilitation at the main campus 179 of this tertiary care center, will qualify to participate in the study prior to beginning Phase II cardiac rehabilitation. Current Facebook users were chosen as it is important that participants 180 181 are skilled at using the internet and familiar with social media. Regular use will be defined as logging onto Facebook at least 2 times in the last month. Inclusion criteria will include both men 182 and women 18 years of age or older who speak English and live within 100 miles of the main 183 campus of this tertiary care center. Participants must be able to read and understand English in 184

order to read the information sheet and complete the Psychological Need Satisfaction in Exercise
Scale (PNSE) [37] and the Behavioral Regulation in Exercise Questionnaire-3 (BREQ-3). There
will be no exclusion based on secondary diagnosis; however, participants must be able to
exercise well enough to qualify to take part in cardiac rehabilitation.

189 Measures

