190 The primary hypothesis, change in motivation for exercise, will be measured at baseline and post-intervention using the BREO-3. The BREO-3 is a 24 question validated instrument that 191 measures forms of intrinsic and extrinsic regulation of exercise behavior [34] and is based on 192 193 self-determination theory. Psychometrics were first completed for the BREQ-2 by Markland and Tobin [38]. Cronbach's alpha reliabilities were as follows: amotivation = 0.83, external 194 regulation = 0.79, introjected regulation = 0.80, identified regulation = 0.73, and intrinsic 195 regulation = 0.86. The BREO-3 includes 5 additional questions in addition to those on the 196 BREQ-2 and has a new subscale for integrated regulation [33]. The subscales (regulations) of 197 the BREQ-3 are used to calculate a relative autonomy index (RAI) [39]. Each question is 198 answered on a 5 point Likert scale (0-4) and represents one of the regulations. The regulations 199 are weighted then summed to give a single score. The resulting score or index gives an 200 201 indication of the individual respondent's self-determination for exercise.

The RAI will place individual motivational subtypes or behavioral regulations on the self-determination continuum from amotivated (lacking intention to exercise) to intrinsically motivated (self-determined or autonomously motivated).

The PNSE will be used to assess need satisfaction with exercise. This scale was designed to assess the perception of psychological need satisfaction associated with self-determined

207	motivation for exercise and consists of 18 items on a 6 point Likert scale, with 3 subscales
208	measuring perceived competence, autonomy, and relatedness. The scale showed high internal
209	consistency (Cronbach >0.90) [37].

The secondary hypothesis, the percentage of cardiac rehabilitation sessions attended, will be measured at the time of cardiac rehabilitation completion or dropout. It will calculated by dividing the number of sessions attended in a 3 month period of time by the total number of sessions allowed by insurance, and multiplying by 100.

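### The primary motivation reading is taken at completion or dropout, so its timing follows attendance; a 12-week reading for everyone would be a cheap, minor improvement

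*Combined protocol and SAP*

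**What the plan says.** Data Collection Procedures gives the only trigger for the post questionnaires: "Upon cardiac rehabilitation completion or dropout, post-data will be collected". Measures adds no time: "The primary hypothesis, change in motivation for exercise, will be measured at baseline and post-intervention".

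A duration of about 12 weeks appears in three other places, none of which sets an assessment time for BREQ-3 or PNSE:

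- Study Objectives describes change "in patients with CHD during a 12-week Phase II cardiac rehabilitation program". This is the length of the programme.
- Setting and Sample says that most patients, "depending on insurance coverage, will be able to attend up to 3 sessions per week for a total of" 36. This is a maximum pace.
- Measures defines attendance from the "number of sessions attended in a 3 month period of time", and the Abstract says "The total number of sessions attended at the end of 3 months will be tallied and" analysed. This is the counting period for sessions.

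Figure 3 (Study Calendar) places intake data in study months 2 to 7 and exit data in months 4 to 11. These are trial months, not weeks of a participant's follow-up.

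Hypothesis 2 predicts an effect on attendance: "Percentage of cardiac rehabilitation sessions attended will be higher relative to a" comparison group. Data Analysis evaluates the RAI by ANCOVA and gives no rule for readings taken at different times.

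**The concern.** Dropout, and possibly time to completion, are parts of attendance, and they decide when the primary questionnaire is answered. Reading time is therefore settled after randomisation by something the intervention is meant to change. Randomisation does not balance it. Adding the observed reading time to the ANCOVA would not be a clean repair, because that time may itself be an effect of treatment.

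If motivation changes over the weeks of the programme, a difference between arms in mean reading time enters the RAI contrast together with any effect on motivation. The Sample Size section says the pilot should estimate the differences on which a larger trial will be designed. A larger trial that copied this schedule would keep the same shift with a narrower confidence interval.

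Variable insurance coverage, listed under Limitations, also spreads the completion times. It is not affected by allocation, so it adds no expected difference between arms.

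**Working it through.** **The plan's own figure.** With 30 per arm, d = 0.8, two-sided 0.05 and df = 58, the two-sample t-test has power 86.1%. The stated 86% is reproduced.

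**Precision.** The 95% CI half-width for an unadjusted mean difference, with all 60 analysed, is t(0.975, 58) × √(2/30) = 0.517 SD. Baseline adjustment would narrow it by an amount the documents do not allow us to compute.

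**Time implied for completers.** 36 sessions at 3 a week take 36/3 = 12 weeks, which agrees with the 12-week programme. At an assumed 2.5 or 2 a week they would take 36/2.5 = 14.4 or 36/2 = 18 weeks. The documents do not say whether sessions may run past 12 weeks.

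**Assumed inputs.** The documents give no dropout rate, dropout week, attendance pace or expected gain. For illustration, assume dropout of 20% (Facebook) and 40% (comparison), all at week 4; a linear gain common to both arms, and to dropouts and completers, of 0.4 or 0.8 SD over 12 weeks; and no treatment effect.

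**Formulas.** Mean reading week = (1 − dropout) × completion week + dropout × 4. False difference = (gain/12) × (Facebook mean week − comparison mean week).

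**Main case: completers in both arms read at week 12.**

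- Facebook: 0.8 × 12 + 0.2 × 4 = 10.40 weeks.
- Comparison: 0.6 × 12 + 0.4 × 4 = 8.80 weeks.
- Difference: +1.60 weeks.
- Gain 0.4 SD: 0.4/12 × 1.60 = +0.053 SD; chance of rejection 5.5% instead of 5%.
- Gain 0.8 SD: 0.8/12 × 1.60 = +0.107 SD; chance of rejection 6.9%.

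**Dependence on completion time**, with the same dropout and the linear gain assumed to continue past week 12:

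| Completion week, Facebook / comparison | Mean weeks | Difference | Gain 0.4 | Gain 0.8 |
|---|---|---|---|---|
| 12 / 12 | 10.40 v 8.80 | +1.60 | +0.05 | +0.11 |
| 14.4 / 14.4 | 12.32 v 10.24 | +2.08 | +0.07 | +0.14 |
| 18 / 18 | 15.20 v 12.40 | +2.80 | +0.09 | +0.19 |
| 12 / 14.4 | 10.40 v 10.24 | +0.16 | +0.01 | +0.01 |
| 12 / 18 | 10.40 v 12.40 | −2.00 | −0.07 | −0.13 |

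When both arms complete at the same pace, the arm with fewer dropouts is read later. With Facebook completers at week 12, the sign changes only if comparison completers take more than (10.40 − 0.4 × 4)/0.6 = 14.67 weeks.

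**If motivation stays flat after dropout**, a dropout's exit reading equals the week-12 reading. With completers at week 12, the false difference is then zero.

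**The case against.** The strongest reply is that the schedule has a natural reading. Follow-up ends at about 12 weeks or at earlier dropout, since the programme lasts 12 weeks and Measures takes attendance at the same completion-or-dropout point over a 3-month period. On that reading, motivation at programme exit is a legitimate target for an intervention tied to the programme, and an arm difference that arises through retention is a real effect. This stands in part: on-schedule completers do have an implied time, and the sponsor may want the exit reading. But the plan does not declare exit as the target. The natural reading also leaves dropouts read whenever they leave.

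It can also be said that the illustration builds in its own bias, because it lets dropouts keep gaining at the attenders' rate. That is correct. If motivation levels off at exit, the early-dropout component disappears.

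A reader might infer that the bias could run strongly in either direction. The documents do not support that. A reversal needs comparison completers to finish well after Facebook completers, beyond 14.67 weeks in the example, and nothing in the plan says sessions may run that long. At 18 weeks, the latest intakes would not fit between the end of month 7 and the end of month 11 (4 × 365.25/12/7 = 17.4 weeks). Nor do the rows above form an envelope, since the 20% v 40% dropout is held fixed throughout.

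A reader might also infer that the primary comparison is invalid. At 5.5% to 6.9% rejection in the main case, and with feasibility as the pilot's first aim, that is too strong.

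**Conclusion.** The point holds as a minor design weakness. In the visible text, the time of the primary reading depends on attendance, attendance is expected to differ by arm, and the analysis has no rule for unequal reading times. The RAI contrast may therefore include a timing difference; the documents do not show that it will.

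If the arms differ only in dropout, the arm with fewer dropouts is read later on average. Under the main-case assumptions the false difference is about 0.05 to 0.11 SD, against a half-width of about 0.52 SD. All inputs to that range are assumed, and the true size cannot be computed from the documents.

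Figure 2, cited at the randomisation step, is not shown in the text available. If it states an assessment week for every participant, what remains is to reconcile it with the completion-or-dropout rule.

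**What to change.** Send the post BREQ-3 and PNSE to every randomised participant, whatever their attendance, at 12 weeks from an anchor date with a stated window, and make this the primary reading. Fix the anchor at allocation: the scheduled programme start where already booked, otherwise the date of randomisation. Do not move it afterwards. Later attendance then cannot shift it, and randomisation need not wait for a booking. The delivery route exists already, since participants receive the "baseline BREQ-3 questionnaire and PNSE scale in the email link that will follow the information" sheet.

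Keep the completion-or-dropout reading for a sensitivity analysis and for use when the 12-week reading is missing. Report time from anchor to assessment, and response, by arm.

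The cost is one extra short emailed questionnaire for those whose exit falls outside the window. Some dropouts will not answer, and their non-response may depend on adherence, which is why the exit reading is kept. Slow attenders will be read before they finish, so the primary result describes motivation at a fixed time rather than at exit. The sample size is unchanged. The calendar has room: from the last intake to the end of exit collection is about 17.4 weeks, leaving 17.4 − 12 = 5.4 weeks for any wait between intake and programme start.

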# **Figure 3**. Study Calendar

Month 1	Month 2-7	Month 4-11	Month 4-12	Month 12
Begin recruitment.	Collection of	Collection of	Data cleaning	Statistical
Complete intake for	intake data	exit data		Analysis.
first 8 subjects				Begin
(BREQ-3, PNSE). No				manuscript
data used for first 8				writing and
subjects				preparation
				for longer
				trial

335

# 336 Data Analysis

337	Statistical Methods. This is a feasibility study and the sample size obtained will determine if
338	the study is appropriately powered to detect the desired effect size. Patient characteristics will be
339	summarized by group using frequencies and percentages for categorical factors, and means and
340	standard deviations for continuous measures. In order to examine the primary outcome,
341	differences in change in motivation between groups, overall motivation using the RAI from the
342	BREQ-3 will be evaluated using analysis of covariance (ANCOVA) models. Mean differences
343	with 95% confidence intervals for group differences will be presented. Multivariate analysis of
344	variance models will be used to evaluate differences in the change across individual motivation
345	subtypes (regulations), using the BREQ-3, between groups overall. If significant, separate
346	ANCOVA models for each subtype will be fit. Similar ANCOVA models will be used to
347	compare changes in needs satisfaction scores, overall and separately among the three subscales,
348	between groups. Two-sample t-tests will be used to compare number of sessions completed. As
349	a secondary analysis, the relationships between patient characteristics, "hits" and "likes", and the
350	outcome variables RAI change, number of sessions, and needs satisfaction change will be
351	examined using t-tests and Pearson correlations. The correlation between changes in RAI and

352	needs satisfaction will also be evaluated. Analyses will be performed using SAS software
353	(version 9.4; Cary, NC). An overall significance level of 0.05 will be assumed for all tests.
354	Sample Size. The investigators plan to enroll 30 patients in each group. In the first 9 months of
355	2016, cardiac rehabilitation at the main campus of this tertiary care center had approximately 170
356	patient intakes. It is assumed that there will be a similar number of patient intakes for a 9 month
357	period in 2017. Based on Facebook participation rates for those over age 50 [21] and the high
358	participation rates in previous research projects in this facility's cardiac rehabilitation, it is
359	estimated that 40% may meet eligibility requirements and agree to participate. Allowing for use
360	of the first 8 participants to establish the Facebook group, the estimated sample size would then
361	be 60 total participants for randomization to study group who can then be included in
362	analysis. With this sample size, there will be 86% power to detect large effect sizes (d=0.8) for
363	our study outcomes [40]. The primary aim of this sample size determination is to evaluate
364	whether the proposed intervention is feasible, and to estimate the differences that might exist so
365	that a larger trial that would have adequate power to detect smaller differences could be designed
366	based on what was learned in this pilot study. The sample size of 30 per group was chosen
367	primarily to facilitate a large intervention group, since the value of the intervention is predicated
368	upon interaction among the participants.

369 Human Subjects Protection

This feasibility study has been approved by the Institutional Review Board of this tertiary
care center (Study #16-1456) and is registered at ClinicalTrials.gov, identifier number
NCT02971813.

Participants will be assured that participation in the study at all times is voluntary and will not affect their care in any way. Protection of human subjects for this study will be further ensured through the use of an information sheet. Participants and those in the comparison group will be informed that privacy of medical information will be ensured. However, due to the nature of social media, information or comments posted by the patients in the Facebook group will be visible to others in the group as well as the study team. For this reason, the information sheet will address the fact that comments may be seen by others.

All responses from participants on the Facebook group will be assigned a number and all other identifying information will be removed for data analysis. Any data on paper will be kept in the PI's locked office in a locked filing cabinet. All electronic data will be stored on the PI's computer which requires password entry and in a folder accessible only to the PI and the research team, and on an encrypted thumb drive. Dissemination of findings will be de-identified and reported numerically, in narrative form or in aggregate, with no personal identifiers.

386

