### **115** Theoretical Framework

The current study is grounded in self-determination theory [29, 30, 20] which defines motivation in terms of intrinsic and extrinsic sources (**Figure 1**). Self-determination theory focuses on social and cognitive factors and how those factors influence an individual's motivation. The theory describes motivation as being on a continuum, with behavioral regulators ranging from amotivation, in which a person lacks intention to do an activity, to intrinsic motivation in which an individual may do the activity simply for the joy of it [20]. Selfdetermination theory specifically examines conditions that lead to self-determined motivation

123	(internalized) and states that 3 psychological needs are necessary for it to exist: competence,
124	autonomy and relatedness [20]. A motivationally supportive environment supports these three
125	needs in several ways. Competence, in essence self-efficacy, can be supported through provision
126	of structure, offering participants positive feedback and helping them to set realistic goals [31,
127	32, 33]. Competence, according to Cognitive Evaluation Theory, a sub-theory of self-
128	determination theory, will not lead to intrinsic motivation in the absence of autonomy [34].
129	Autonomy may be supported by helping the individual make decisions for personal reasons and
130	helping them to make choices with minimal pressure [31, 32, 33]. Relatedness can be promoted
131	by providing a sense of connectedness to others. An environment that helps a person feel
132	socially included and supported by others may help facilitate intrinsic motivation [20, 32, 35].
133	Motivation for exercise is an important concept in the examination of cardiac
134	rehabilitation adherence. Self-determination theory was previously used as a theoretical
135	framework for motivational research in a cardiac rehabilitation setting [36]. Thorup and
136	colleagues [36] showed qualitative evidence that a pedometer-based cardiac rehabilitation
137	intervention supported autonomy, competence, and relatedness. It is possible that increasingly
138	more self-determined motivation (internalized) may be enough to help patients overcome the
139	many obstacles associated with non-adherence to exercise and cardiac rehabilitation.

140 **Figure 1.** Self-Determination Theory

Amotivation; External Regulation; Introjected Regulation; Identified Regulation; Integrated Regulation; Intrinsic Regulation

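### The six BREQ-3 subtype ANCOVAs are fitted only after a significant MANOVA, so no adjusted subtype estimate is planned when it fails, and small or moderate effects are overstated when it passes

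*Combined protocol and SAP*

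**What the plan says.** The protocol's Data Analysis section (Statistical Methods) compares overall motivation, the RAI, by ANCOVA without any precondition. It then plans a MANOVA on change in the individual regulations, and the per-regulation models follow only on a condition: "subtypes (regulations), using the BREQ-3, between groups overall. If significant, separate" ANCOVAs. The Abstract repeats the rule: "motivation subtypes. If significant, ANCOVA models for each subtype will be fit". Neither place says what is reported for the regulations if the condition is not met.

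Four other statements bear on this:

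- Hypothesis 1 in Study Objectives names the regulations as well as the overall score: "Facebook intervention and across individual motivational subtypes (regulations"). The Measures section calls change in motivation the primary hypothesis.
- The promise of estimates stands after the RAI model and before the MANOVA: "with 95% confidence intervals for group differences will be presented. Multivariate analysis of" variance comes next in the text.
- The needs-satisfaction models, including those for three subscales, follow with no gate: "ANCOVA models for each subtype will be fit. Similar ANCOVA models will be used to" compare needs satisfaction.
- The Sample Size section gives the aim of the sample size as to evaluate "whether the proposed intervention is feasible, and to estimate the differences that might exist so" that a larger trial able to detect smaller differences can be designed.

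On multiplicity the plan says only: "An overall significance level of 0.05 will be assumed for all tests".

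**The concern.** A MANOVA followed by univariate models is a familiar testing sequence. Here it also decides whether estimates exist. A pilot that is meant to estimate differences would produce adjusted subtype differences only in the trials where the observed differences happened to be large. Two things follow.

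1. When the MANOVA fails, the subtype part of hypothesis 1 may end with little more than a non-significant p-value.
2. When it passes, the estimates are too large on average and the intervals cover less often than stated. This is worst for the smaller effects that the later trial is supposed to be powered for.

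The RAI cannot fill the gap. It is a weighted sum of the regulations and does not show which of them moved.

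**Working it through.** **Inputs from the protocol.** 30 per group and 60 analysed (Sample Size); six regulations (Figure 1); significance level 0.05, taken as two-sided; d=0.8 with 86% power (Sample Size).

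**Inputs assumed, because the documents give none.** Normal subscales with SD 1; correlation 0.3 between subscales; baseline-post correlation r = 0.3/0.5/0.7; no dropout. Triplets below follow that order of r.

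**Step 1: the plan's own figure.** A two-sided two-sample t-test with 30 per group and d=0.8 has noncentrality 0.8 × √15 = 3.10 on 58 df. Its power is 86.1%, so the stated 86% is reproduced. It applies to one two-group comparison, not to the MANOVA.

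**Step 2: how often the gate passes.** With two groups and six change scores, the MANOVA is an exact F test on 6 and 53 df, with 5% critical value 2.275. Change scores have covariance 2(1−r)R, where R is the subscale correlation matrix. The noncentrality is λ = 15 × δ′R⁻¹δ / [2(1−r)].

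- One subtype at 0.4: the diagonal element of R⁻¹ is (1/0.7)(1 − 0.3/2.5) = 1.257. So λ = 15 × 0.16 × 1.257 / [2(1−r)] = 2.16/3.02/5.03, and the gate passes in 14/19/30%.
- All six at 0.4: the elements of R⁻¹ sum to 6/2.5 = 2.4. So λ = 15 × 0.16 × 2.4 / [2(1−r)] = 4.11/5.76/9.60, and the gate passes in about 25/35/56%.
- One subtype at 0.8: λ is four times the first case, 8.62/12.07/20.11, and the gate passes in about 51/68/91%.

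In every case with an effect of 0.4 here except the last (all six, r=0.7), the more likely outcome is that no adjusted subtype model is fitted.

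**Step 3: what the estimates look like once it passes.** In simulated trials, each post score was regressed on group and its own baseline. Excess is (mean estimate − truth)/truth, computed before rounding.

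| True effect | Mean estimate after passing | Excess | 95% CI coverage |
|---|---|---|---|
| One subtype at 0.4 | 0.58/0.57/0.53 | 44/42/32% | 87/89/92% |
| All six at 0.4 | 0.53/0.51/0.46 | 31/26/16% | 91/92/94% |
| One subtype at 0.8 | 0.91/0.88/0.82 | 14/10/3% | – |
| Three or six at 0.8 | – | 4% or less | – |

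Fitted in every trial, the same ANCOVAs average 0.40 and 0.80 with about 95% coverage. Their expected 95% half-width is t(0.975, 57) × √[(2/30)(1−r²)] = 0.49/0.45/0.37 SD.

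**Step 4: sensitivity.**

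- *Pattern along the continuum.* The Theoretical Framework says "The theory describes motivation as being on a continuum". Effects graded from −0.4 to +0.4, with neighbouring subscales correlated 0.6 falling to −0.3 at the ends, pass in 16/22/37%. The end subtypes are then about 43/39/28% too large.
- *24 per arm (assumed 20% loss), one subtype at 0.4.* Passes in 12/15/23%, with excess 53/51/40%.
- *Subscale correlation 0 to 0.5, r = 0.5 or 0.7, one, three or six subtypes affected.* The mean estimate after passing is 1.28-1.85 times the truth at d=0.2, 1.09-1.65 at 0.3, 1.00-1.39 at 0.5 and 1.00-1.14 at 0.8.

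**Step 5: what the gate does for error control.** If no subtype changes, at least one of six unadjusted tests is significant in about 24% of trials without the gate and 3.6/3.8/4.2% with it. If one subtype truly changes by 0.8, a false positive among the other five occurs in about 21% without the gate and still in 14/17/20% with it. Holm over the six without the gate gives 4.6-4.8% there. Power for the changed subtype is 50/66/90% with the planned gate, 44/62/88% with gate plus Holm, and 69/79/94% with Holm alone.

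**The case against.** The strongest defence has four parts.

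- **Little hangs on the subtypes.** The estimation aim in the Sample Size section does not mention them, and Study Objectives bases feasibility on sample size and engagement. The RAI, attendance and needs satisfaction, which are likelier to size a larger trial, are all ungated. This stands and keeps the point minor. A reader might infer that the primary measure, or the pilot's estimates generally, are biased by the gate. The documents do not support that: only the subtype ANCOVAs are conditional.
- **Subtype results might still appear after a failed MANOVA.** The MANOVA always runs, and it rests on the six between-arm differences in mean change. Reported every time, these would be unbiased, though less precise than ANCOVA. A reader might infer that the plan forbids showing them; it does not. Nor does it provide for them, and on its closest reading the confidence-interval sentence covers the RAI only. What is missing from the plan is the baseline-adjusted subtype difference.
- **The gate is a recognised, prespecified guard against false positives.** This is true when no subtype changes. Once one does, the protection is weak (Step 5).
- **Any significance filter inflates estimates.** With one subtype at 0.4 and no gate, estimates that reach Holm significance average 0.78/0.72/0.61, more inflated than the gated ones. This stands. Reporting all six removes the bias only if none is singled out for being significant.

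**Conclusion.** The point holds and is minor. That no adjusted subtype estimate is planned after a non-significant MANOVA follows from the text and needs no assumption. The size of the overstatement after a significant one depends on correlations and effects that the documents do not give. It is material for small or moderate effects, roughly a third to just under a half for one subtype at 0.4 SD under the main assumptions. It is small at d=0.8, and negligible wherever the gate almost always passes.

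The subtypes are part of the primary hypothesis, so they should not be treated as a side analysis. The primary measure within that hypothesis, the RAI, is nevertheless untouched. A reader might also infer that the gate should be kept and reinforced with Holm. The figures do not support this: anything rejected by gate plus Holm is also rejected by Holm alone, so the combination can only lose power, and Holm alone already holds familywise error at about 5%.

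**What to change.** Amend the Statistical Methods and the Abstract so that:

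1. All six subtype ANCOVAs are fitted whatever the MANOVA result, each adjusted for that subtype's own baseline score. All six mean differences are reported with 95% confidence intervals, labelled exploratory, with none singled out for being significant.
2. The MANOVA supports only the overall claim that the subtypes differ between groups.
3. Claims about single subtypes are either not made or rest on Holm over the six without the gate.

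The cost is a few sentences and up to six models on data already collected. There are two downsides. The six intervals carry no multiplicity adjustment. If Holm is used, per-subtype power falls against the planned unadjusted gate when several subtypes change: with three at 0.8, about 73/82/95% against 81/92/99%. The planned gate's higher power there comes with weaker error control.
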